8.1.4.1. Patient-reported Change in Severity of Adhesive Capsulitis

The Patient-reported Change in Severity of Adhesive Capsulitis is a questionnaire that asks subjects if their AC symptoms are "Better, About the Same, or Worse" since the last time the questionnaire was administered. Subjects who report that their symptoms are better or worse are then asked to rate the change in their symptoms on a 7-point ordinal scale.

All subjects will complete the Patient-reported Change in Severity of Adhesive Capsulitis questionnaire at times outlined in the Schedule of Activities. The Patient-reported Change in Severity of Adhesive Capsulitis questionnaire answers will be entered by the subject directly into an eCOA instrument while the subject is alone with no study site personnel in the room.

8.1.5. Subject Satisfaction with Treatment

Subjects will rate their satisfaction with treatment on a 5-point Likert scale from Very Dissatisfied to Very Satisfied at times specified in the Schedule of Activities. The response will be entered directly into an eCOA instrument and completed while the subject is alone with no study site personnel in the room. The subject will be instructed to refrain from discussing their rating with the investigator and any other site personnel.

8.1.6. Investigator Assessment of Improvement with Treatment

Investigators will provide their assessment of improvement with treatment for each subject using a 7-point Likert scale from Very Much Worse to Very Much Improved at times specified in the Schedule of Activities. The response will be entered directly into an eCOA instrument. The investigator will refrain from discussing their rating with the subject.

8.1.7. Magnetic Resonance Imaging and X-rays

MRIs of the affected and contralateral shoulder will be performed for all subjects at times specified in the Schedule of Activities. Subjects should complete all other screening activities, including an X-ray of the affected shoulder, prior to the MRIs required at screening, and must meet the entry criteria of passive external rotation assessment at 0° , 45° , and 90° abduction and have an adapted ASES function subscale score (< 35) in the affected shoulder prior to the conduct of the screening MRIs. Previous X-rays of the affected shoulder may be used if they were taken within 30 days of the Screening Visit.

Additionally, subjects must be able (in a supine position) to have the affected arm passively externally rotated to at least a neutral position within the subject's level of pain tolerance with the elbow at the side (against the body) and flexed to 90° prior to the MRI at screening.

A central MRI committee consisting of 2 blinded musculoskeletal radiologists who will serve as the primary readers and 1 blinded clinician who will serve as the adjudicator in discordant cases. All screening MRIs of the affected shoulder will be reviewed through a blinded central read, performed by specialists with expertise in musculoskeletal imaging to determine if the subject has any clinically significant confounding pathologies and to confirm subject eligibility. MRI-based determinations of eligibility made by the central MRI committee are final, and will supersede any previous MRI analyses made by investigational site personnel or MRI imaging center personnel.

Specific instructions for the MRI procedures will be provided in the Study Operations Manual. All MRIs from this study are the property of Endo and de-identified images may be utilized for clinical development, scientific communication, marketing, regulatory purposes, and/or legal applications as required/desired by Endo.

8.2. Safety Assessments

All safety assessments will be performed at the times outlined in the Schedule of Activities. Additional (unscheduled) safety assessments may be performed as needed.

In order to ensure subject safety and protect data integrity, Endo, in accordance with the *FDA Guidance on Conduct of Clinical Trials of Medical Products during COVID-19 Public Health Emergency* (March 2020, updated 02 July 2020), will allow virtual visits for safety assessments. In addition, subjects impacted by the health emergency will be allowed to continue in the study and complete remaining dosing and assessments when the investigational sites re-open.

8.2.1. Demography

The subject's birth date, gender, race, and ethnicity will be collected at screening.

8.2.2. Medical and Surgical History

Medical and surgical history will be obtained at the Screening Visit. Medical history will include a review of the following systems: general, dermatological, respiratory, cardiovascular, gastrointestinal, genitourinary, gynecological, endocrine, musculoskeletal, hematological, neuropsychological, immune (allergies), and head, eyes, ears, nose, and throat. Historical and current medical conditions, including date of last menstrual period for female subjects, will be recorded.

In addition, any history or current collagen mediated disorders (including but not limited to Garrod's pads, Dupuytren's nodules, plantar nodules, PD, AC of other joints, etc) will be recorded (excluding the current AC episode).

History of tobacco and alcohol use (never, current, former) will also be collected.

Surgical history will include a review of all surgical procedures completed in the prior 5 years and any surgery completed at any time in the affected shoulder.

8.2.3. Adhesive Capsulitis History

A history of all past episodes of AC of the shoulder will be recorded at screening. Details of each past episode to be collected include: the affected shoulder (right or left), onset date, resolution date, and any procedures or medical treatments provided.

In addition, the history of the current AC episode including the affected shoulder (right or left), onset date of symptoms, and determination of idiopathic or traumatic AC will be recorded at screening.

8.2.4. Physical Examination

The complete physical examination will include evaluation of the head, eyes, ears, nose, throat, neck (including thyroid), cardiovascular system (including assessment of heart, peripheral

22 October 2021

pulses, presence or absence of edema), lungs, abdomen (including liver and spleen, bowel sounds), lymph nodes, musculoskeletal system (including spine, joints, muscles), neurological system (including cranial nerves, reflexes, sensation, strength), skin, extremities, and other conditions of note.

All examinations will be performed by a physician or health professional listed on the Form FDA 1572 and licensed to perform physical examinations. The investigator will review all physical exam findings for clinical significance. Any new, or change from the Screening Visit in, physical examination findings that is considered by the investigator to be clinically significant will be recorded as an AE (or SAE, if appropriate).

Any clinically significant physical exam finding will be recorded as medical history at screening.

8.2.5. Height and Weight

Height will be collected at screening only. Weight will be collected as outlined in the Schedule of Activities. Any change from the Screening Visit in subject weight that is considered by the investigator to be clinically significant will be recorded as an AE (or SAE, if appropriate).

8.2.6. Vital Signs

Vital signs will be obtained after the subject has been seated for 5 minutes (minimum) and will include systolic and diastolic blood pressures, pulse rate, respiratory rate, and body temperature. The results, date, and time for all vital sign assessments will be recorded.

On days that study treatment is administered (the Day 1, 22, and 43 Visits), vital signs will be taken up to 4 hours prior to dosing and at 15 and 30 minutes after dosing (body temperature is not required at the 15-minute postdose time point). The subject's vital signs must be stable, or repeated until stable, before the subject can leave direct observation.

The investigator will review all vital sign values for clinical significance. Any change from the Screening Visit in vital signs that is considered by the investigator to be clinically significant will be recorded as an AE (or SAE, if appropriate).

8.2.7. Electrocardiogram

A 12-lead ECG recording will be conducted at the Screening Visit. The subject should be in a supine position for at least 5 minutes before the recording is conducted. Lead position will be that of a standard 12-lead ECG; no additional or special lead placements will be necessary.

If the ECG report shows QT prolongation (QTc \ge 450 ms for males or QTc \ge 470 ms for females), the investigator will exclude the subject from study participation.

The investigator will review all ECG results for clinical significance. Any ECG result meeting the investigator's criteria for clinical significance will be recorded as an AE (or SAE, if appropriate).

8.2.8. Clinical Laboratory Determinations (Chemistry, Hematology, Urinalysis, HbA1c, TSH, Serum and Urine Pregnancy Test)

Blood and urine samples will be collected for clinical laboratory testing at the time points outlined in the Schedule of Activities. Required clinical laboratory tests are outlined

22 October 2021

in Section 10.2. Clinical laboratory tests will be performed by a designated central laboratory. Each site will be provided with instructions on specimen collection, preparation, packaging and transport. The results of the tests will be returned to the investigational sites.

Samples for laboratory testing may be collected under fasted or nonfasted conditions. The date and time of the sample collection must be documented on the laboratory report. Investigators must review and sign laboratory reports and document the clinical significance of each laboratory abnormality. New clinically significant laboratory abnormalities or clinically significant changes in laboratory values will be reported as AEs (or SAEs, if appropriate).

Clinical laboratory test data will be reviewed by the investigator, or designee, and additional clinical laboratory tests may be ordered at his/her discretion. Any additional testing will be performed by the designated central laboratory.

8.2.9. Pregnancy Testing

All female subjects of childbearing potential will have serum and/or urine pregnancy tests performed at the time points outlined in the Schedule of Activities. Results must be available prior to protocol mandated study treatment administration. Subjects with positive results at the Screening Visit or the Day 1 Visit will be ineligible for study entry. Any female subject that becomes pregnant during the study will be immediately discontinued from study treatment, but may continue in the study (see Section 7.1). All pregnancies will be reported as per Section 8.3.5.

If applicable, the subject's agreement to use contraception throughout their study participation (from Screening to the Day 95 Visit), or for 28 days after the last dose of study treatment for subjects who early terminate, will be documented.

8.3. Adverse Events and Serious Adverse Events

The definitions of AEs and SAEs can be found in Section 10.3.

All AEs and SAEs, including both observed or volunteered problems, complaints, signs, or symptoms must be recorded, regardless of whether associated with the use of study treatment. This would include AEs resulting from concurrent illness, reactions to concurrent medication use, or progression of disease states (excluding the disease under study). A condition present at baseline that worsens after initiation of study treatment will be captured as an AE; the onset date will be the date the event worsened. The AE should be recorded in standard medical terminology when possible.

8.3.1. Time Period and Frequency for Collecting AE and SAE Information

All AEs and SAEs will be collected by the investigator from the time of signing the informed consent form (ICF) through the Day 95 Visit, or for 28 days after the last dose of study treatment for those who early terminate.

Investigators are not obligated to actively seek AEs and SAEs after conclusion of subject study participation. However, if the investigator learns of any SAE, including death, at any time after the subject has been discharged from the study, and the investigator considers the event to be reasonably related to the study treatment or study participation, the investigator must notify the sponsor within 24 hours as described in Section 10.3.

22 October 2021

All SAEs will be recorded and reported to the sponsor or designee within 24 hours, as indicated in Section 10.3. The investigator will submit any updated SAE data to the sponsor within 24 hours of it being available.

The method of recording, evaluating, and assessing causality of AEs and SAEs and the procedures for completing and submitting SAE reports are provided in Section 10.3.

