 - ^f Subject must be able (in a supine position) to have the affected arm passively externally rotated to at least a neutral position within the subject's level of pain ^c All patient-reported outcomes (PROs) must be completed prior to study assessments/ beginning of visit. Must be completed and criteria met prior to MRI. tolerance with the elbow at the side (against the body) and flexed to 90° .
 - AROM measurements must be completed before PROM measurements.
- ¹ Serum pregnancy assessment will not be done on the Day 95 Visit.
- Must be completed prior to MRI. Previous X-rays of the affected shoulder may be used if they were taken within 30 days of the Screening Visit.
- Subjects must complete supervised in-office PT 2 days per week for 2 weeks after each treatment session. Subjects must wait a minimum of 7 days after each treatment session prior to starting PT and there should be a minimum of 2 days between PT sessions.
 - Home exercises will be completed at least 2 times per day and no more than 3 times per day, every day starting 3 days after each dose of study treatment through the Day 95 Visit. In-office PT will count as 1 of the home exercise sessions on PT days.
- AEs/SAEs will be captured from time of informed consent signature until the Day 95 Visit or for 28 days after last dose of study treatment for subjects who discontinue early from the study. There is no time limit on collection of SAEs assessed as related to study treatment.

Note: Unless otherwise stated above, all assessments should be completed prior to dosing on treatment days (the Day 1, 22, and 43 Visits)

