6.1.1. Dose Interruption

All eligible subjects will receive their first dose of study treatment on Day 1. At each subsequent treatment visit (the Day 22 and 43 Visits) each subject will be evaluated to determine if they can continue treatment.

Subjects that have all 5 measurements of AROM and PROM (forward flexion, internal rotation, external rotation, abduction, and shoulder extension) of the affected shoulder that are > 90% of the baseline contralateral shoulder ROM and have an adapted ASES function subscale score of > 40 in affected shoulder should not be dosed unless the investigator believes that the clinical benefit outweighs the risk.

Subjects who are not treated at the Day 22 Visit will continue in the study and will be reassessed at the Day 43 Visit and may be treated based on these assessments and investigator discretion. Subjects who are not treated at the Day 22 and/or Day 43 Visits will complete all other activities required for those visits and are also expected to complete the Day 64 and Day 95 Visits.

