7.2. Subject Withdrawal from the Study

Subjects may withdraw from the study at any time at their own request, or may be withdrawn at any time at the discretion of the investigator for safety, behavioral, compliance, or administrative reasons. The date of withdrawal and the reason for withdrawal will be recorded.

If the subject withdraws consent for disclosure of future information, the sponsor may retain and continue to use any data collected before such withdrawal of consent. If a subject withdraws from the study, the subject may request destruction of any biological samples taken and not yet tested. The investigator must document this in the site study records.

A subject may be discontinued from the study for the following medical or administrative reasons:

- Withdrawal by subject (reason must be specified).
- An AE.
- Death.
- A protocol violation (reason must be specified, for example: lack of compliance, use of a prohibited concomitant medication, etc).
- The subject was lost to follow-up.
- Other reasons (reason must be specified, for example: the subject moved, pregnancy, investigator decision, sponsor decision to terminate trial, etc).

If a subject discontinues from the study, all early termination procedures should be conducted as detailed in the Schedule of Activities. The date a subject discontinues and the reason for discontinuation will be recorded in the source documentation and electronic case report form (eCRF). If, however, a subject withdraws consent, no additional procedures are required. This information should be recorded in the source documentation and the eCRF.

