8. STUDY ASSESSMENTS AND PROCEDURES

Study procedures and their timing are summarized in the Schedule of Activities (Section 1.2). Adherence to the study design requirements, including those specified in the Schedule of Activities, is essential and required for study conduct. Protocol waivers or exemptions are not

allowed. Activities outlined in the Study Operations Manual must be followed or will result in a protocol deviation.

Urgent safety concerns should be discussed with the sponsor immediately upon occurrence or awareness to determine if the subject should continue study treatment and/or be withdrawn from the study.

All screening evaluations must be completed and reviewed to confirm that potential subjects meet all eligibility criteria. The investigator will maintain a screening log to record details of all subjects screened and to confirm eligibility or record reasons for screen failure, as applicable.

Passive External Rotation at 0°, 45°, and 90° of Abduction

Passive external rotation at 0° , 45° , and 90° of abduction will be measured in both shoulders using a goniometer at screening in the supine position. In the event that 45° and 90° cannot be achieved due to pain or restriction in the affected shoulder, the amount of external rotation available at maximum attainable abduction ROM is permissible as the second and third measurements.

Hand Dominance

The subject's self-reported hand dominance will be recorded at screening.

Supervised In-office Physical Therapy

All subjects will undergo a standard supervised in-office PT regimen. The PT regimen will consist of 2 sessions per week for 2 weeks starting 7 days after each study treatment until the next scheduled injection and until the Day 64 Visit. In-office PT will last approximately 30 to 60 minutes. Subjects will be provided with verbal and hands-on instructions for the exercises to be completed. Physical therapists will follow the standard PT regimen found in the Study Operations Manual. All subjects will continue the PT regimen regardless of dose interruption or withdrawal from the study.

Home Exercises

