8.3.3. Follow-up of AEs and SAEs

After the initial AE/SAE report, the investigator is required to proactively follow each subject at subsequent visits/contacts. All nonserious AEs must be followed until resolution or until the last study visit whichever comes first; except for subjects who withdraw early from the study for whom nonserious AEs will be followed until resolution or for 28 days after the last administration of study treatment, whichever comes first.

All SAEs and nonserious AESIs will be followed to resolution, stabilization, the event is otherwise explained, or until follow-up is no longer possible. Further information on follow-up procedures is provided in Section 10.3.

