3.16.1. Adverse Events

All adverse events (AEs) will be recorded from the time informed consent is signed through the Day 95/ET Visit, or for 28 days after the last dose of study treatment for those who early terminate.

Conditions existing prior to screening will be recorded as part of subject's medical history.

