4. STUDY PARAMETERS

4.1. Subject Disposition

A subject will be considered to have completed the study if the subject has completed the Day 95 Visit.

Subjects who discontinue or are withdrawn from the study treatment for any reason will be encouraged to complete the remaining study visits and evaluations and provide any additional follow-up information as required by the study unless the subject specifically indicates that they will not participate in any further evaluations. The reason and date for study treatment discontinuation will be recorded in the eCRF.

If a subject withdraws from the study, all early termination procedures will be conducted as detailed in the SoA (Table 2). The reason and date for early withdrawal will be recorded in the eCRF for subjects who do not complete the study. If, however, a subject withdraws consent, no additional procedures are required except the collection of AE information. This information will be recorded in the source documentation and the eCRF.

Subjects who have been withdrawn from the study at any time after the first dose of study treatment will not be replaced. The reason for screen failure will also be recorded in the eCRF for subjects who consent to participate in this study but are not subsequently randomized.

4.2. **Protocol Deviations**

Potential deviations will be identified prior to database lock. Protocol deviations will be derived from the eCRF data, electronic vendor data and will be obtained from the clinical monitoring reports. All deviations from these sources will be reconciled and duplicate deviations will be removed.

Possible protocol deviations include, but are not restricted to the following deviation types:

- Ineligible subject/study entry criteria not satisfied.
- Informed consent not completed correctly.
- Non-compliance of study treatment.
- Prohibited medications/procedure.
- Visit/procedure missing or out of window.

The Endo study team will approve all final protocol deviation assignments and classify them as either major or minor during ongoing protocol deviation review meetings held throughout the study and a final meeting prior to the database lock.

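### For early terminators the AE window ends 28 days after the last dose with no later-of clause, so read literally it can close before study exit, in conflict with the text that has AEs recorded throughout

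*Protocol*

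**What the plan says.** **Collection.** Protocol 8.3.1 runs AE and SAE collection from consent "through the Day 95 Visit, or for 28 days after the last dose of study treatment for those who early terminate". Footnote l of the protocol's Schedule of Activities has the same rule: "AEs/SAEs will be captured from time of informed consent signature until the Day 95 Visit or for 28 days after last dose", the latter for subjects who leave early. SAP Table 2 footnote l repeats it. SAP 3.16.1 names the combined Day 95/ET Visit as the end point but then keeps the clause "or for 28 days after the last dose of study treatment for those who early terminate".

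**Follow-up.** For subjects who withdraw early, protocol 8.3.3 says "nonserious AEs will be followed until resolution or for 28 days after the last administration of study treatment, whichever comes first". SAEs and nonserious AESIs are not capped in this way. They are followed until they resolve, stabilize or are otherwise explained, or until follow-up is impossible.

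**Time on study after the last dose.** Protocol 6.1.1 allows injections to be withheld: "Subjects who are not treated at the Day 22 and/or Day 43 Visits will complete all other activities required for those visits", and such subjects are expected at Days 64 and 95 as well. Section 6.1 keeps a subject on study when the arm position does not permit injection. Section 7.1 encourages subjects who stop treatment to complete the remaining visits.

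**Text pointing the other way.** The AE row of the Schedule spans the whole study. Section 8.3 requires all AEs to be recorded, 8.3.2 has subjects asked about AEs at every visit, and 10.3.4.1 has AEs documented for the duration of the study.

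**Two neighbouring inconsistencies.** On withdrawal of consent, protocol 7.2 says "If, however, a subject withdraws consent, no additional procedures are required", whereas SAP 4.1 says "no additional procedures are required except the collection of AE information". On physical therapy, protocol section 8 says "All subjects will continue the PT regimen regardless of dose interruption or withdrawal from the study", with a parallel sentence for home exercise, whereas SAP 3.14 ends home exercise at the Day 95/ET Visit.

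**The concern.** A 28-day tail after the last dose works as an extension for someone who leaves soon after an injection. It works badly as an end date for someone who leaves long after one, because it then falls before the exit. Without a later-of clause, the text does not say which of these is meant.

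Safety is a named objective. SAP 7.10.2 compares the proportions of subjects with AEs between arms by Fisher's exact test, and the TEAE definition in SAP 4.8.1.1 has no end date. Whether a late event is counted therefore depends on whether the site recorded it. Two sites could each follow the documents and treat the same event differently. Time at risk for recorded events would then vary with dosing history, with early exit and with site practice. Amendment 4 was prompted by early termination running above expectation, so the clause is not a remote case.

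**Working it through.** The plan states no figure to reproduce here; the check is calendar arithmetic followed by a comparison of passages.

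**Inputs.** Injections on Day 1, Day 22 (+3 days) and Day 43 (+3 days), from the Schedule. A tail of 28 days from the last dose, from 8.3.1 and 8.3.3. Illustrative exit days 64, 80 and 94; these are my choice and not in the documents.

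**Formulas.** Closing day = last dose day + 28. Uncovered on-study days = exit day − closing day, or 0 if negative.

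| Last dose | Window closes | Exit Day 64 | Exit Day 80 | Exit Day 94 |
|---|---|---|---|---|
| Day 1 | Day 29 | 35 | 51 | 65 |
| Day 22 to 25 | Day 50 to 53 | 11 to 14 | 27 to 30 | 41 to 44 |
| Day 43 to 46 | Day 71 to 74 | 0 | 6 to 9 | 20 to 23 |

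For example, last dose on Day 22 and exit on Day 80: 22 + 28 = 50, and 80 − 50 = 30 days. The rows correspond to one, two and three injections when these are given in sequence. A subject who misses Day 22 but is injected on Day 43 belongs in the last row.

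**Which events are exposed.**
- Collection: only events starting after the closing day. Footnote l puts no time limit on SAEs assessed as related, so what remains is nonserious AEs and SAEs not assessed as related.
- Follow-up: only nonserious events that are not AESIs. If such an event starts on Day 50 in a subject injected only on Day 1 who leaves on Day 60, the follow-up limit in 8.3.3 was Day 29, which is 50 − 29 = 21 days before onset.

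**Scale.** Planned drop-out is about 20%: 0.20 × 180 = 36, or 180 − 142 = 38 from the completion target. This is an upper bound at the planned rate. The affected subset is those who leave more than 28 days after their last dose, and the documents do not give its size.

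**After the fix.** If the window ends at the later of the Early Termination Visit and last dose + 28, uncovered on-study days are 0 in every cell. For anyone leaving within 28 days of a dose, nothing changes.

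**The case against.** The strongest reply is that nobody is an early terminator until they leave. Until then, collection through Day 95 governs, AEs are asked about at each visit, and nothing tells a site to delete an event on exit. Section 8.3.1 itself ties the end of active seeking to the end of participation, and SAP 3.16.1 names the ET Visit. On this view the 28-day clause only extends collection for people who leave soon after a dose.

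Much of this stands. It is a sensible reading, and it means that many late events would be recorded anyway. It does not remove the defect, because 8.3.1 and footnote l state a different end date for these subjects, 8.3.3 says whichever comes first, and SAP 3.16.1 keeps the last-dose clause next to the ET Visit. The sensible reading has to be inferred against the stated date.

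A reader might infer more than the documents support:
- *That on-study events are lost.* The record-throughout passages make loss possible, not certain.
- *That the arms are ascertained differently.* Withholding depends on recovery criteria and can be overridden by the investigator. No frequency by arm is given.
- *That the contrast in observation after the last dose measures the problem.* A fully dosed completer is seen for 95 − 43 = 52 days after the last dose and an early leaver is covered for 28, but most of that gap comes from leaving early. Under the fix, a fully dosed subject leaving on Day 60 would still stop at Day 71.
- *That only leavers have unresolved events without an outcome.* Under 8.3.3, completers' nonserious AEs also stop being followed at the last study visit.

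**Conclusion.** The point holds as a faulty end date that contradicts other text in the same documents. On the literal wording, any exit more than 28 days after the last dose falls after the window has closed, by up to 65 days for a subject injected only on Day 1 who leaves on Day 94. The exposure is limited to nonserious AEs and unrelated SAEs starting after that date for collection, and to nonserious non-AESI events for follow-up.

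This rests on nominal dosing days plus the +3-day windows, and on reading the clause as written. The documents show neither lost data nor a difference between arms, and they do not give the number of subjects affected. The correction is worth making because the rule feeds a planned between-arm comparison and is easily repaired.

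The consent and exercise mismatches are real but separate: they do not depend on the last-dose anchor. The consent difference is not among the changes from protocol listed in SAP section 8.

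**What to change.** In protocol 8.3.1 and Schedule footnote l, and in SAP 3.16.1 and Table 2 footnote l, state that collection runs to the Day 95 Visit or, for subjects who terminate early, to the later of the Early Termination Visit and 28 days after the last dose. Use the same end date for follow-up of nonserious AEs in protocol 8.3.3.

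Separately:
- reconcile protocol 7.2 with SAP 4.1 on AE collection after withdrawal of consent;
- reconcile the protocol section 8 sentences on physical therapy and home exercise after withdrawal with SAP 3.14.

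**Cost.** A short protocol amendment, which under section 10.1.1 needs IRB/IEC approval before use, and matching SAP edits. No visit is added, since Early Termination procedures already exist. Early leavers who exit more than 28 days after their last dose would have a somewhat longer AE record.
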